2.3.1 Potential Mechanism of Action

ATG appears to induce both generalized immunosuppression and immunoregulation⁴⁷. The drug consists of polyclonal antibodies against thymocytes and also targets other immune cells. It prevents B-cell proliferation and differentiation and mediates T-cell suppressive effects via inhibition of proliferative responses to mitogens^{48,49}.

Preclinical data, although limited, support the mechanisms observed in study participants, and demonstrate that low-dose ATG has multiple beneficial mechanistic actions (e.g., increased Treg:Teff ratios, reduced islet inflammation, improved beta cell area, etc.). Notably, early changes in the Treg/Teff ratio (at 3 months post therapy) were predictive of response to therapy (AUC C-peptide) at 2 years in the TN19 clinical trial

In humans, a “standard dose” of ATG (10-15 mg/kg) reduces the total lymphocyte count by more than 85%. T-cell depletion may result from complement-dependent opsonization and cellular lysis, Fc-dependent opsonization, or Fas-mediated apoptosis. Fas-mediated apoptosis is likely the more predominant mechanism at lower ATG concentrations, where ATG exhibits preferential effects on pre-activated, as opposed to nonactivated, T-cells. It has been hypothesized that ATG administration may induce a population of CD8+, CD57+CD28- T cells that have regulatory effects on CD4+ Th1 cells that may enable autoimmune destruction of beta cells⁴⁴. Total lymphocyte and CD8+ T cell counts typically return to normal within 2 months of ATG administration, whereas CD4+ T cell counts can remain reduced for 12 months. These effects may explain the lasting immune-modulatory activity of ATG. Following ATG infusion, the CD4:CD8 T cell ratio remains significantly and persistently lower, relative to baseline values, and the CD4:CD8 ratios often correlate with graft survival and rejection rates in transplantation studies⁵⁰⁻⁵³.

[figure not shown]
Other studies have suggested alternative mechanisms underlying the beneficial ATG effects. Like anti-CD3, ATG may induce partial T-cell activation, leading to an anergic state⁵⁴⁻⁵⁷. In cynomolgus monkeys, ATG appears to coat T cells, leading to downregulated surface expression of CD2, CD3, CD4, and CD8 molecules, along with impaired immune responses in mixed lymphocyte reactions³⁶. In addition, antibodies to adhesion molecules may interfere with cellular adhesion and endothelial interactions, as well as T-cell migration to sites of inflammation. ATG may also prevent T cell co-stimulation by binding directly to APC, and may induce complement-mediated lysis of these cells; particularly in more mature APC⁵⁸. The survival of immature dendritic cells (DC) thus may be more tolerogenic. Antigens recognized by ATG include CD86, CD32, CD4, CD11b, CD29, and CD51/61; some of which are shared by lymphocytes and DC. In addition, ATG contains antibodies that cross-react with B-cell surface antigens, promoting activated B cell apoptosis⁵⁹⁻⁶¹.

2.3.2 Safety and efficacy experience of ATG in Children with Stage 3 T1D:

Prospect of direct benefit for children with Stage 2 T1D

ATG has been standard of care for induction therapy for pediatric renal transplant recipients for nearly 20 years and has been administered to hundreds of people at doses that are 5-7 times higher (10-15mg/kg) than is proposed for treatment of Stage 2 diabetes in this protocol (2.5mg/kg)⁶². There is also extensive experience with its use in children for treatment of transplant rejection⁶³. The North American Pediatric Renal Trials Collaborative Studies registry (n=455) demonstrated that doses of <7.5mg/kg of ATG prevent renal transplant loss safely and effectively⁶⁴. Similarly, a study of 235 pediatric renal transplant recipients following ATG at doses < 4.5mg/kg revealed the even lower dose provided safe and effective immunosuppression versus higher doses⁶⁵. The adverse events were managed with standard therapies used in other settings. At the proposed and higher doses, the adverse events were reversible.

The TrialNet TN19 trial enrolled participants with new onset Stage 3 T1D between the ages of 12-45 years and was not powered to compare age groups as a pre-specified analysis. However, in a post-hoc analysis comparing participants less than or greater than age 18, the C-peptide and HbA1c responses were at least as robust, if not more so, in children versus adults (**Fig 11**). This provides additional strong support for prospect of benefit when considering the use of low-dose ATG to prevent progression from Stage 2 to Stage 3 T1D in children.

Adverse events previously reported in studies of low dose (2.5 mg/kg) ATG in new-onset T1D (ages 12–45 years) included transient cytokine release syndrome (CRS), lymphopenia and serum sickness⁶⁶. Notably, these side effects were similar in frequency and severity when comparing children to adults in the TN19 study. There were no reported cases of diabetic ketoacidosis nor severe hypoglycemia in the TN19 trial participants^{44,66}.

In the adult population (18-45 years) of participants treated with ATG monotherapy (n=10) in the TN19 study, no serious adverse events were reported. 51 non-serious adverse events were reported in adult receiving ATG monotherapy. 75.5% of those events were assessed as related to ATG treatment. The most commonly reported non-serious adverse events in adults were decreased lymphocyte count, serum sickness, fever and cytokine release syndrome (Table 2).

TABLE 2: Non-Serious Adverse Events Reported in TN19 Study for Participants Ages 18-45					
		Attribution #			
Systems Affected (CTC 4.0)		Non-serious - related		Non-serious - unrelated	
Category	AE term	Number of Participants	Number of Adverse Events	Number of Participants	Number of Adverse Events
Endocrine disorders	Hypothyroidism	0	0	1	1
General disorders and administration site conditions	Fever	2	4	0	0
	General disorders and administration site conditions - Other, specify	1	3	0	0
	Infusion site extravasation	1	1	0	0
Immune system disorders	Cytokine release syndrome	3	3	0	0
	Serum sickness	7	7	0	0
Infections and infestations	Sinusitis	1	1	0	0
	Upper respiratory infection	1	2	1	1
Investigations	CD4 lymphocytes decreased	5	5	0	0
	Lymphocyte count decreased	8	8	0	0
Metabolism and nutrition disorders	Metabolism and nutrition disorders - Other, specify	0	0	1	2
Musculoskeletal and connective tissue disorders	Arthralgia	1	1	0	0
	Bone pain	1	1	0	0
	Myalgia	2	2	0	0
Neoplasms benign, malignant and unspecified (incl cysts and polyps)	Neoplasms benign, malignant and unspecified (incl cysts and polyps) - Other, specify	0	0	1	1
Nervous system disorders	Tremor	0	0	1	1
Psychiatric disorders	Depression	0	0	1	1
Respiratory, thoracic and mediastinal disorders	Cough	0	0	2	2
	Nasal congestion	0	0	1	1
Skin and subcutaneous tissue disorders	Skin and subcutaneous tissue disorders - Other, specify	0	0	2	2
Surgical and medical procedures	Surgical and medical procedures - Other, specify	0	0	1	1

In the pediatric population (12-17) of participants treated with ATG only, a total of 4 serious adverse events were reported with only 2 considered related to study agent (ATG); 1 report of vasovagal reaction and 1 report of serum sickness (Table 3). All adverse events reported for the ATG only treated participants from the TN19 study (serious and non-serious) are included in the TrialNet IB addendum.

TABLE 3: Serious Adverse Events Reported in TN19 Study for Participants Ages 12-17					
Systems Affected (CTC 4.0)		Attribution #			
		Serious - related		Serious - unrelated	
Category	AE term	Number of Participants	Number of Adverse Events	Number of Participants	Number of Adverse Events
Immune system disorders	Serum sickness	1	1	0	0
Injury, poisoning and procedural complications	Injury, poisoning and procedural complications - Other, specify	0	0	1	1
Nervous system disorders	Vasovagal reaction	1	1	0	0
Surgical and medical procedures	Surgical and medical procedures - Other, specify	0	0	1	1

In the pediatric population, 115 non-serious adverse events were reported. Of those 115 non-serious adverse events, 89 were assessed as related to ATG treatment (77.4%). The most commonly reported non-serious adverse events in the pediatric population were serum sickness, cytokine release syndrome, decreased lymphocyte counts, headache and decreased white blood cell count (Table 4).

TABLE 4: Non-Serious Adverse Events Reported in TN19 Study for Participants Ages 12-17					
Systems Affected (CTC 4.0)		Attribution #			
		Non-serious - related		Non-serious - unrelated	
Category	AE term	Number of Participants	Number of Adverse Events	Number of Participants	Number of Adverse Events
Blood and lymphatic system disorders	Blood and lymphatic system disorders - Other, specify	1	1	0	0
Gastrointestinal disorders	Abdominal pain	2	3	0	0
	Dyspepsia	1	1	0	0
	Nausea	1	1	0	0
	Toothache	0	0	1	2
	Vomiting	0	0	2	2
General disorders and administration site conditions	Chills	1	1	0	0
	Fatigue	1	1	0	0
	Fever	2	2	0	0
	Flu like symptoms	2	3	0	0
	General disorders and administration site conditions - Other, specify	1	1	1	1
	Pain	2	2	0	0
Immune system disorders	Cytokine release syndrome	11	14	0	0
	Serum sickness	13	13	0	0
Infections and infestations	Otitis media	0	0	1	1
	Pharyngitis	1	1	0	0

TABLE 4: Non-Serious Adverse Events Reported in TN19 Study for Participants Ages 12-17					
		Attribution #			
Systems Affected (CTC 4.0)		Non-serious - related		Non-serious - unrelated	
Category	AE term	Number of Participants	Number of Adverse Events	Number of Participants	Number of Adverse Events
	Rash pustular	0	0	1	1
	Skin infection	0	0	1	1
	Upper respiratory infection	0	0	2	2
	Urinary tract infection	0	0	1	1
Injury, poisoning, procedural complications	Fracture	0	0	1	1
Investigations	CD4 lymphocytes decreased	8	9	1	1
	Investigations - Other, specify	1	1	0	0
	Lymphocyte count decreased	11	13	0	0
	Neutrophil count decreased	2	3	1	1
	White blood cell decreased	4	5	0	0
Metabolism and nutrition disorders	Hypoglycemia	0	0	1	2
Musculoskeletal / connective tissue disorders	Pain in extremity	1	1	0	0
Nervous system disorders	Headache	3	9	0	0
	Nervous system disorders - Other, specify	0	0	1	1
Skin and subcutaneous tissue disorders	Rash maculo-papular	1	1	0	0
	Skin and subcutaneous tissue disorders - Other, specify	1	1	3	7
	Urticaria	0	0	2	2
Vascular disorders	Hypotension	1	1	0	0
	Phlebitis	1	1	0	0

In summary, clinical trial data from two independent studies in Stage 3 T1D have demonstrated efficacy in preserving C-peptide and lowering A1c in persons and suggest equal if not greater effects on metabolic responses in children compared to adults ^{6,61}.

In the 2023 published case study, similar side effects were experienced in 6 pediatric participants who presented as at-risk for developing stage 3 T1D. CRS was reported in half of these participants and all had experienced serium sickness. No additional drug-related adverse events beyond CRS and SS were reported. 3 participants remained diabetes-free at 18 months, 3 years and 4 years respectively after treatment with ATG².

2.4 The unmet need for T1D therapies in children

Stage 3 T1D has its highest incidence in children ages 6 to 12 years, with a smaller peak later in adolescence. The hypothesis to be tested in the proposed clinical study is that ATG treatment will delay or prevent the diagnosis of Stage 3 diabetes in adults and children with high-risk, i.e. with Stage 2 diabetes. The immediate unmet clinical need for therapies that can delay or prevent Stage

3 T1D is emphasized by studies showing that even the most advanced insulin replacement therapeutic regimens have poor uptake in children with Stage 3 T1D⁶⁷. Adolescents with diabetes also are the population that has the most sub-optimal glycemic control with mean HbA1c concentrations, even when under the care of endocrinologists, of > 9%⁶⁸. Elevated HbA1c levels over time are associated with the risk of secondary end-organ complications including eye, kidney, and neurologic diseases⁶⁹. The poor clinical outcomes of metabolic control and long duration of exposure to poor metabolic control are thought to be the basis for the observed loss of life expectancy of more than a decade, compared to non-diabetic peers, for individuals diagnosed with Stage 3 T1D as children⁷⁰. Thus, the need for agents to delay and/or prevent progression from Stage 2 to Stage 3 T1D is most urgent for the pediatric population in order to reduce the time of exposure to poor metabolic control, a direct benefit to pediatric participants.

There are other immediate benefits of delay or prevention of Stage 3 diabetes for children and their families: These include avoiding daily repeated injections with insulin or use of mechanical devices, monitoring of glucose levels, constraints the diagnosis imposes on spontaneous activity. These quality-of-life aspects were recently highlighted during the FDA advisory panel meeting regarding the approval of teplizumab as a therapy to delay progression from Stage 2 to Stage 3 T1D (May 27, 2021). Any meaningful delay in the time to progression from Stage 2 to Stage 3 provides time for a child to and their families to better adapt to the lifestyle changes needed to cope with intensive insulin management. Likewise, advances in treatment of the disease including additional immunomodulatory interventions and automated insulin delivery are moving forward such that that delays in progression from Stage 2 to Stage 3 may permit persons with diabetes to take advantage of future therapies that are best suited for those who still retain some degree of endogenous beta cell function.

There are also important practical limitations in performing a prevention study with ATG that only enrolls adults. It would take many years to identify and enroll a sufficient number of adults to determine whether the treatment will alter progression from Stage 2 to Stage 3 T1D diagnosis – in the TN10 trial, previously completed by TrialNet, it took 1 year to enroll 6 people with diabetes over the age of 18. In addition, the time from Stage 2 to the diagnosis of Stage 3 diabetes is longer in adults compared to children, meaning it might take 5-8 years to detect a signal of meaningful delay in a study that was required to only enroll high-risk adults. Furthermore, participation in studies seeking to delay progression from Stage 2 to Stage 3 T1D is known to markedly reduce the incidence of diabetic ketoacidosis in children who do progress to Stage 3.

In summary, T1D is a disease that must be meaningfully studied in children to develop therapeutics capable of delaying progression from Stage 2 to Stage 3 disease. Preclinical studies support the ability of ATG to delay or prevent disease onset at a time when beta cell destruction is thought to be most active (i.e. Stage 2 diabetes in humans). In addition, both preclinical and clinical data have shown that ATG can slow the progression of autoimmune diabetes. The safety profile of low-dose ATG is well described with adverse event frequencies that are manageable and similar in children and adults. The disease course in adults is more protracted and the data from treating people with Stage 3 T1D with ATG suggest that the efficacy might be superior in children versus adults. Meanwhile children have the most urgent unmet need for agents that can delay or prevent Stage 3 diabetes because of their risk of secondary end-organ complications due to prolonged life exposure to dysglycemia, their observed shortened life expectancies, and the disease burden faced by people with T1D and their families. Recent experience in off-label treatment of ATG in pediatric participants at-risk of progression to Stage 3 T1D further demonstrates the tolerability of of ATG treatment in children as young as 5 years and the potential for low-dose ATG to meaningfully delay progression to Stage 3 T1D. As such, failing to enroll children in the proposed

trial would delay testing of ATG in this clinical setting and potentially deprive children of a treatment that may indeed be beneficial.

Given the totality of the available safety, efficacy, risk, and benefit data associated with low-dose ATG, and the fact that the Stages of T1D represent a continuum of the same disease process rather than different disease, statutory direct prospect of benefit requirements have been met for children to receive low-dose ATG as a potential means of preventing or delaying progression from Stage 2 to Stage 3 T1D.

3 STUDY DESIGN

3.1 Overview

This study is a 2-arm, multi-center, double blinded, 2:1 randomized, placebo-controlled clinical trial. The trial will investigate whether intervention with ATG will delay or prevent progression to Stage 3 T1D in individuals identified with a 2-year 50% risk for progression to Stage 3 T1D. A total of 101 people with 2-year 50% risk of progression to T1D will be enrolled. The treatment phase will consist of 2 infusions over 2-3 days. Participants will be followed up for at least 24 months from randomization. Participants who progress to stage 3 T1D will be followed to explore the treatment effect on C-peptide retention for at least one year.

3.1.1 Inclusion Criteria

Potential participants must **meet all** the following inclusion criteria:

1. Willing to provide informed consent or have a parent or legal guardian provide informed consent when the participant is <18 years of age.
2. Age ≥ 6 and < 35 years
3. At least two or more diabetes-related biochemical autoantibodies (mIAA, GADA, ICA, IA-2A, ZnT8A) present on the same sample. In the absence of other antibodies, ICA and GADA positivity alone will not suffice for eligibility in this trial.
4. Weight greater than the 5th percentile for age and sex.
5. BMI < 95th and > 5th percentile for age for those under age 18 years and < 30 and > 15 for adults (≥ 18)
6. ADA Stage 2 criteria* **AND** at least one of the following high-risk markers (occurring at the same visit) within 7 weeks (52 days) of randomization, defined below (for defining a 2-year 50% risk for progression to Stage 3 T1D):
 - a. HbA1c ≥ 5.7 and <6.5%
 - b. Index60 ≥ 1.4
 - i. $\text{Index60} = 0.3695 \times (\log \text{fasting C-peptide [ng/mL]}) + 0.0165 \times 60\text{-min glucose (mg/dL)} - 0.3644 \times 60\text{-min C-peptide (ng/mL)}$
 - c. DPTRS ≥ 7.4

$$\text{DPTRS} = (1.57 \times \log \text{BMI}) - (0.06 \times \text{age}) + (0.81 \times \text{glucose sum from 30 to 120 min/100}) - (0.85 \times \text{C-peptide sum from 30 to 120 min/10}) + (0.48 \times \log \text{fasting C-peptide})$$

*Dysglycemia is defined as 2-hr glucose ≥ 140 and <200 mg/dL or fasting glucose ≥ 110 and <126 or 30, 60, or 90 minute glucose ≥ 200 mg/dL from OGTT⁷.

7. CMV and/or EBV seronegative participants must be CMV and EBV PCR negative within 30 days of randomization and may not have had signs or symptoms of a CMV or EBV-compatible illness lasting longer than 7 days within 30 days of randomization.
8. CMV seropositive participants must be CMV PCR negative and all EBV seropositive participants must have EBV PCR < 2,000 IU/mL within 30 days of randomization and may

not have had signs or symptoms of a CMV or EBV-compatible illness lasting longer than 7 days within 30 days of randomization.

9. Seated blood pressure less than 130/80 mmHg for participants ≥ 18 years. For participants < 18 years seated blood pressure less than 95th percentile for age, sex and height.
10. Be at least 4 weeks from last live immunization.
11. Participants are required to receive non-live influenza vaccination at least 2 weeks prior to randomization when vaccine for the current or upcoming flu season is available.
12. Participants must have a negative COVID-19 test within 7 days of the first day of treatment if otherwise eligible.
13. Willingness to comply with study directed social distancing and protection from SARS-Cov-2 infection.
14. Be willing to forgo vaccines (other than killed influenza) during the 3 months after study drug treatment period (Days 0 and 1).
15. Be up to date on all recommended vaccinations based on age of participant*
16. With the exception of stage 2 T1D, participants must be healthy, as defined by absence of any other untreated diagnoses that the protocol committee deems to be a potential confounder.
17. If a female participant with reproductive potential, willing to avoid pregnancy (abstinence or adequate contraceptive method) through the completion of the study infusions and up to 3 months after study drug administration and undergo pregnancy testing prior to each study visit.
18. Must be residing or have accommodations within 1 hour of the infusion site during the two days of study drug infusions and must be within 1 hour of a medical care facility for 1 day after completion of infusion 2.
19. Participants must live in a location with rapid access to emergency medical services.

* Adult participants must be fully immunized. Pediatric participants who have not completed their primary vaccination schedule must receive all vaccinations allowable per the national/country-specific immunization guidelines for their current age prior to study drug delivery. Any remaining vaccinations should be given and continue per the schedule at least 3 months after study drug is administered. For COVID-19 vaccination, all participants will be strongly encouraged to be up-to-date with COVID-19 vaccine(s) as indicated by country-specific guidelines at least 2 weeks prior to randomization.

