21. Any condition that in the investigator's opinion may adversely affect study participation will be reviewed by the Study Chair to ensure consistency and adjudicate whether or not the participant may compromise the study results

22. Any screening/baseline laboratory result not otherwise stated out of normal reference range and/or medical history that may increase the risk of the participant's participation in this trial.
23. Previously diagnosed with Stage 3 T1D according to ADA criteria⁷ (*see Appendix 3 for Criteria for diagnosis of diabetes*)

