4.3 Randomization and Treatment Masking

Eligible study participants will be randomized in a 2:1 allocation to either ATG or placebo treatment arms by the TrialNet Coordinating Center at the baseline visit once eligibility has been confirmed. Prior to randomization, participants will have a random glucose measurement to check their dysglycemic state has not progressed towards Stage 3 T1D. As long as this random glucose check is less than 200, randomization will proceed. If the value exceeds 200, the study physician will need to perform a safety check for Stage 3 T1D.

Randomization will be conducted using block randomization with stratification by whether the participant is less than 18 years of age or 18 years and older. Participants will be assigned a study randomization number corresponding to the treatment group assignment.

All participants and study personnel apart from the study pharmacist will be masked to the contents of the infusion. Treatment masking is inclusive of the ATG/Hydrocortisone/Heparin infusion or placebo infusion. Similarly, the premedication administration of methylprednisolone/placebo will also be masked. The only active therapeutics that all participants will receive regardless of randomization are the unmasked pre-infusion medications acetaminophen and diphenhydramine (a comparable antihistamine may be substituted for diphenhydramine in countries where it is unavailable).

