8.1 Primary Outcome and Analyses

The primary outcome is the elapsed time from random treatment assignment to the development of diabetes or time of last contact among those randomized.

Criteria for stage 3 diabetes onset are, as defined by the American Diabetes Association (ADA), based on glucose testing, or the presence of unequivocal hyperglycemia with acute metabolic decompensation (diabetic ketoacidosis) as defined below:

1. Unequivocally symptomatic* AND at least one of the following:

1. Random glucose ≥ 200 mg/dl [11.1 mmol/L] OR
2. Fasting glucose ≥ 126 mg/dl [7 mmol/L] OR
3. OGTT = diabetic OR
4. HbA1c $\geq 6.5\%$

* Unequivocal symptoms: severe/persistent polyuria, polydipsia and/or significant unexplained weight loss

2. If not unequivocally symptomatic, two separate objective measures are required for diagnosis. These tests must occur at least one day apart but as soon as possible and must be consecutive, defined as without an intervening non-diabetic OGTT.

1. The preferred object measures for diagnosis are:

1. 2 diabetic OGTTs, not on the same day (the confirmatory OGTT is the date of diagnosis)
2. However, if an individual is diagnosed without the consecutive OGTTs, the following also constitutes diagnosis in TrialNet:
 1. Diabetic OGTT + FPG ≥ 126 mg/dl [7 mmol/L] not on the same day
 2. Diabetic OGTT + HbA1c $\geq 6.5\%$ (these may be on the same day)
 3. FPG ≥ 126 mg/dl [7 mmol/L] + HbA1c $\geq 6.5\%$ (these may be on the same day)

It is preferred that OGTTs for Stage 3 T1D diagnosis are analyzed using TrialNet laboratories. If a participant has an OGTT that indicates diabetes (clinical alert), the site should invite the participant for a repeat OGTT as soon as possible. To make a diagnosis of Stage 3 T1D diabetes, each of two consecutive OGTTs must meet diabetes criteria. Thus, if the second OGTT does not confirm the diagnosis, the participant will continue to be followed in the ATG Low-Dose Prevention Study and will be asked to return for the next follow-up visit. At that time, the OGTT will be repeated and, if indicative of diabetes, will need to be performed a second time to confirm the diagnosis.

In the case of symptoms or unequivocal hyperglycemia with acute metabolic decompensation (diabetic ketoacidosis), repeat testing is not required to confirm the diagnosis of Stage 3 T1D and prompt evaluation and initiation of clinically indicated treatment will occur.

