APPENDIX 3: Criteria for the Diagnosis of Diabetes⁷

A1C $\geq 6.5\%$ (≥ 48 mmol/mol). The test should be performed in a laboratory using a method that is NGSP certified and standardized to the DCCT assay.*

OR

FPG ≥ 126 mg/dL (≥ 7.0 mmol/L). Fasting is defined as no caloric intake for at least 8 h.*

OR

2-h PG ≥ 200 mg/dL (≥ 11.1 mmol/L) during OGTT. The test should be performed as described by the WHO, using a glucose load containing the equivalent of 75 g anhydrous glucose dissolved in water.*

OR

In an individual with classic symptoms of hyperglycemia or hyperglycemic crisis, a random plasma glucose ≥ 200 mg/dL (≥ 11.1 mmol/L). Random is any time of the day without regard to time since previous meal.

DCCT, Diabetes Control and Complications Trial; FPG, fasting plasma glucose; OGTT, oral glucose tolerance test; NGSP, National Glycohemoglobin Standardization Program; WHO, World Health Organization; 2-h PG, 2-h plasma glucose. *In the absence of unequivocal hyperglycemia, diagnosis requires two abnormal test results obtained at the same time (e.g., A1C and FPG) or at two different time points.

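### Criterion 6 does not apply its own upper glucose and HbA1c limits on every entry route, so a single unconfirmed diabetic-range result does not prevent randomisation

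*Combined protocol and SAP*

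**What the plan says.** Criterion 6 in section 3.1.1 asks for ADA Stage 2 criteria plus "at least one of the following high-risk markers (occurring at the same visit) within 7 weeks (52 days) of randomization". The markers are HbA1c ("HbA1c ≥ 5.7 and <6.5"), Index60 and DPTRS, and any one suffices. The footnote on dysglycemia reads "Dysglycemia is defined as 2-hr glucose ≥ 140 and <200 mg/dL or fasting glucose ≥ 110 and <126" and continues "or 30, 60, or 90 minute glucose ≥ 200 mg/dL from OGTT". The synopsis in section 1.1 has the same structure. Table 1 in section 2.2 bounds Stage 2 at fasting glucose 100–125 mg/dL, 2-hour glucose 140–199 mg/dL and HbA1c 5.7–6.4%.

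Four other provisions bear on the same candidate:

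- Exclusion 23 (section 3.1.2) removes anyone "Previously diagnosed with Stage 3 T1D according to ADA criteria". Appendix 3 says that, without unequivocal hyperglycemia, "diagnosis requires two abnormal test results obtained at the same time (e.g., A1C and FPG) or at two different time points".
- Section 4.3 adds a random glucose check before randomisation: "As long as this random glucose check is less than 200, randomization will proceed". A higher value leads to a physician's check for Stage 3.
- The footnote on the OGTT row of Appendix 1 asks that an OGTT consistent with diabetes be repeated as soon as possible, aiming for within a month.
- Section 8.1 defines the endpoint in a person without symptoms by two consecutive measures on separate occasions, preferably "2 diabetic OGTTs, not on the same day (the confirmatory OGTT is the date of diagnosis", although some pairs that include HbA1c may fall on the same day. Consecutive means only that no non-diabetic OGTT lies between them. Cases with a single objective measure go to the Eligibility and Events Committee.

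**The concern.** The trial tests whether ATG delays the move from Stage 2 to Stage 3. If the upper limits bind only inside separate alternatives, someone can enter who already has one of the two results that would diagnose Stage 3. Two things are then at stake.

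The first is consistency. One site may read the Stage 2 label as imposing Table 1's limits, while another applies the footnote literally. Adjudicators have no rule on whether the screening test counts towards the endpoint.

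The second is power. The final analysis is triggered by 44 events and the interim by 22. An event that comes at about the first on-study OGTT (month 3) at the same rate in both arms uses up one of those events and pulls the hazard ratio towards 1.

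**Working it through.** **1. Does the text admit such a person?** Three illustrative profiles (assumed values, glucose in mg/dL), each with fasting C-peptide 1.5 and 60-minute C-peptide 4.0 ng/mL. Index60 = 0.3695 × log(fasting C-peptide) + 0.0165 × 60-minute glucose − 0.3644 × 60-minute C-peptide. The protocol does not give the base of the logarithm. The natural log is used here; base 10 lowers each value by less than 0.1.

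| Profile | Dysglycemia met by | Index60 (needs ≥ 1.4) | Diabetic-range result |
|---|---|---|---|
| A: fasting 105, 60-min 230, 90-min 240, 2-hour 215, HbA1c < 6.5% | intermediate value | 0.150 + 3.795 − 1.458 = 2.49 | 2-hour only |
| B: fasting 115, 60-min 190, 2-hour 210, HbA1c < 6.5% | fasting value | 0.150 + 3.135 − 1.458 = 1.83 | 2-hour only |
| C: fasting 105, 60-min 190, 2-hour 160, HbA1c 6.6% | 2-hour value | 1.83 | HbA1c only |

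All three satisfy criterion 6 as written. B and C show that the gap is not confined to the intermediate time points.

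**2. Do the other provisions stop them?**

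- Exclusion 23 with Appendix 3: each profile has one abnormal result, so none is a diagnosis. Two abnormal results at the same visit would be.
- Random glucose: this is neither a fasting nor a timed post-load value, so a person with a 2-hour value of 210 can pass it.
- Repeat-OGTT footnote: a repeat within a month fits inside the 52-day entry window and would usually settle A and B. It is an aim, it is not stated to precede randomisation, and it does not address an isolated HbA1c (C).
- Exclusions 21 and 22 are discretionary.

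What remains is a single unconfirmed diabetic-range result, with no requirement to resolve it first.

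**3. Reproducing the stated power.** Inputs from sections 8.4 and 8.5.2: HR 0.4, 101 participants (68:33), 50% two-year control risk (hazard ln 2 / 2 = 0.347 per year), 4-year accrual, 10% two-year dropout, 44 events, chi-square boundaries 8.78 at 22 events and 3.88 at 44. Simulating this with the log-rank test (6,000 trials, Monte Carlo error about 0.5 point) gives 85.1%. Closed forms bracket it:

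- Schoenfeld, 2:1: Φ(√(44 × 2/9) × |ln 0.4| − 1.96) = Φ(2.865 − 1.96) = 81.7%.
- Freedman, 2:1: c = (1 + 2 × 0.4)² / (2 × 0.6²) = 4.5; Φ(√(44/4.5) − 1.96) = Φ(3.127 − 1.96) = 87.8%.

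**4. Hypothetical worst case.** Let m participants, allocated regardless of arm, have an event at about month 3 with HR 1. In closed form the signal shrinks by (1 − m/44) and the average HR is 0.4^(1 − m/44). The simulated ranges cover two assumptions: the other participants keep a 50% control risk, or the whole cohort does.

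| m | Simulated power | Closed form (Schoenfeld; Freedman) | Average HR |
|---|---|---|---|
| 0 | 85.1% | 81.7%; 87.8% | 0.40 |
| 3 | 80–81% | – | – |
| 5 | 77% | 71.9%; 79.2% | 0.44 |
| 10 | 65–67% | 60.0%; 67.6% | 0.49 |

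Loss per event: (85.1 − 80.2)/3 ≈ 1.6 points and (85.1 − 65.5)/10 ≈ 2.0 points, so about 1.5 to 2.

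**5. If ATG also acts on these people.** Suppose 10% of entrants are affected. With 70% confirming early in both arms, simulated power is 71%. With 70% on placebo and 50% on ATG it is 79%. If ATG lowers early confirmation by the full 60%, nothing is lost.

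**The case against.** The strongest reply is that the protocol already handles this candidate. A diabetic OGTT is to be repeated promptly. If the repeat is diabetic, the person is diagnosed and exclusion 23 applies. If it is not, the first test can no longer pair with a later one under section 8.1. Criterion 6 also cites ADA Stage 2, which could be read as importing Table 1's limits. This largely stands for OGTT results when the repeat is done in time. It does not stand as a rule, because nothing prevents randomisation while the repeat is pending.

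A reader might go further and infer any of the following, which the documents do not support:

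- *People with Stage 3 diabetes are being enrolled.* Without symptoms or unequivocal hyperglycemia, a single abnormal result is not a diagnosis under Appendix 3 or section 8.1.
- *A single month-3 OGTT makes them endpoints.* Section 8.1 is silent on screening tests, and cases with a single objective measure are adjudicated.
- *Their events carry no information because ATG cannot yet have acted.* Section 2.3.1 reports that Treg/Teff changes at 3 months predicted later response, and section 2.3 reports benefit in people already at Stage 3.
- *A large loss of power is expected.* No passage gives the number of such entrants.

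Section 2.2 also states the 50% two-year risk definition without upper limits on fasting or 2-hour glucose, so the planning rate may already include such people.

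**Conclusion.** The eligibility gap is real and follows from the wording alone. Criterion 6 and the synopsis do not hold the document's own limits on every route, in conflict with the Stage 2 label and Table 1. The safeguards narrow the gap to one unconfirmed diabetic-range result without closing it, and section 8.1 leaves open whether that result can be half of an endpoint.

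The consequence for power is conditional. It rests on an unknown number of entrants and on the worst-case assumption that they have early events regardless of arm. Under that assumption, 3 such entrants would bring 85% down to about 80%, and 5 to about 77%. The loss is smaller, or absent, if ATG also delays confirmation. These entrants fall into both arms by randomisation, so the effect is dilution and not a false-positive risk. The point merits a wording change; it does not call for a redesign.

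**What to change.** Reconcile criterion 6, the synopsis, Table 1, exclusion 23 and the repeat-OGTT footnote in one of two ways, the choice being the sponsor's:

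- state that fasting <126 mg/dL, 2-hour <200 mg/dL and HbA1c <6.5%, the limits already in criterion 6, hold on every route at the qualifying visit; or
- state that any diabetic-range screening result must be repeated and resolved before randomisation.

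In section 8.1, state that both measures making up an endpoint diagnosis must be obtained after randomisation.

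The cost is a few sentences. A few candidates will need a repeat test or be excluded, which may slightly slow accrual (section 8.4 expects about 20 candidates a year) and the arrival of events. Because the final analysis waits for 44 events, slower events would lengthen the trial but would not reduce the number of events analysed.
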